Appendix E SF-36 V2 Scoring

General Scoring information

Items and scales are scored in 3 steps:

- Step 1. Item recoding, for the 10 items that require recoding,
- Step 2. Computing scale scores by summing across items in the same scale (raw scale scores); and,
- Step 3. Transforming raw scale scores to a 0-100 scale (transformed scale).

Item recoding

- All 36 items should be checked for out-of-range values prior to assigning the final item value. All out-of-range values should be recoded as missing data.
- The following tables show the recoding of response choice.

How to treat missing data

A scale score is calculated if a respondent answered at least half of the items in a multi-item scale (or half plus one in the case of scales with an odd number of items).

The recommended algorithm substitutes a person-specific estimate for any missing item when the respondent answered at least 50 percent of the items in a scale. A psychometrically sound estimate is the average score, across completed items in the same scale, for that respondent. For example, if a respondent leaves one item in the 5-item mental Health scale blank, substitute the respondent's average score (across the 4 completed mental health items) for that one item. When estimating the respondent's average score, use the respondent's final item values.

Computing raw scale scores

After item recoding, including handling of missing data, a raw score is computed for each scale. This score is a simple algebraic sum of responses for all items in that scale.

If the respondent answered at least 50% of the items in a multi-items scale, the score can be calculated. If the respondent did not answer at least 50% of the items, the score for that scale should be set to missing.

Transformation of the scale scores

The next step involves transforming each raw score to a 0 to 100 scale using the following formula:

$$\text{Transformed scale} = \frac{[(\text{actual raw score} - \text{lowest possible raw score}) / \text{possible raw score range}] \times 100}{100}$$

This transformation converts the lowest and highest possible scores to zero and 100, respectively.

Table 6 - SF-36 V2 raw scores of eight domains

Scale	Lowest and highest possible raw scores	Possible raw score range
Physical Functioning	10,30	20
Role-Physical	4,20	16
Bodily pain	2,12	10
General health	5,25	20
Vitality	4,20	16
Social Functioning	2,10	8
Role-Emotional	3,15	12
Mental Health	5,25	20

Appendix F FACIT-fatigue scoring guidelines (version 4)

- Instructions:*
1. Record answers in "item response" column. If missing, mark with an X
 2. Perform reversals as indicated, and sum individual items to obtain a score.
 3. Multiply the sum of the item scores by the number of items in the subscale, then divide by the number of items answered. This produces the subscale score.
 4. The higher the score, the better the QOL.

Subscale	Item Code	Reverse item?		Item response	Item Score
FATIGUE	HI7	4	-	_____	= _____
	SUBSCALE	HI12	4	-	_____
	An1	4	-	_____	= _____
	An2	4	-	_____	= _____
	An3	4	-	_____	= _____
	An4	4	-	_____	= _____
	An5	0	+	_____	= _____
	An7	0	+	_____	= _____
	An8	4	-	_____	= _____
	An12	4	-	_____	= _____
	An14	4	-	_____	= _____
	An15	4	-	_____	= _____
	An16	4	-	_____	= _____

Sum individual item scores: _____

Multiply by 13: _____

Divide by number of items answered: _____ = **Fatigue Subscale score**

*For guidelines on handling missing data and scoring options, please refer to the Administration and Scoring Guidelines in the manual or on-line at www.facit.org.

Appendix G SAS code for EQ-5D-3L index utility scoring

```
/*=====*/;
/* Aim : Derive the EQ5-D index (utility) */;
/* Source for the algorithm : scoring EQ-5D health states (██████████) */;
/* (cf. G:\_HE\PRO questionnaire\EQ5D\scoring\YorkTariffx.doc) */;
/* Note : UK based population (Dolan, 1997) */;
/* Author : ██████████ */;
/*=====*/;

data EUROQOL; set temp;
profil= (10000*eqq1cd)+(1000*eqq2cd)+(100*eqq3cd)+(10*eqq4cd)+eqq5cd;
eq5d=1;
*****Mobility*****;
if eqq1cd=2 then eq5d=eq5d-0.069;
if eqq1cd=3 then eq5d=eq5d-0.314;
*****Self-care*****;
if eqq2cd=2 then eq5d=eq5d-0.104;
if eqq2cd=3 then eq5d=eq5d-0.214;
*****Usual activities*****;
if eqq3cd=2 then eq5d=eq5d-0.036;
if eqq3cd=3 then eq5d=eq5d-0.094;
*****Pain/discomfort*****;
if eqq4cd=2 then eq5d=eq5d-0.123;
if eqq4cd=3 then eq5d=eq5d-0.386;
*****Anxiety/depression*****;
if eqq5cd=2 then eq5d=eq5d-0.071;
if eqq5cd=3 then eq5d=eq5d-0.236;

if (eqq1cd ne 1 or eqq2cd ne 1 or eqq3cd ne 1 or eqq4cd ne 1 or eqq5cd ne 1)
then eq5d=eq5d-0.081;

if (eqq1cd=3 or eqq2cd=3 or eqq3cd=3 or eqq4cd=3 or eqq5cd=3)
then eq5d=eq5d-0.269;

if (eqq1cd=. or eqq2cd=. or eqq3cd=. or eqq4cd=. or eqq5cd=.)
then eq5d=.;

run;
```

Appendix H SAS code for SF-36 scoring

```
*****
* PROGRAM: SF36 V2
* PURPOSE: SAS SCORING PROGRAM FOR THE SF-36 VERSION2
*
*****;

*****;
*** STEP 1: INPUT DATA ***;
*****;

DATA SF36DATA;
INFILE IN;
INPUT ID $ 1-3
      @ 5 (GH1 HT PF01-PF10 RP1-RP4 RE1-RE3 SF1
          BP1-BP2 VT1 MH1 MH2 MH3 VT2 MH4 VT3 MH5
          VT4 SF2 GH2 GH3 GH4 GH5) (1.);
RUN;

*****;
*** STEP 2: SF-36 SCALE CONSTRUCTION ***;
*****;

*****
* USING THE SAS DATASET CREATED IN PART 1, CHANGE OUT-OF-RANGE
* VALUES TO MISSING FOR EACH ITEM. RECODE AND RECALIBRATE ITEMS
* AS NEEDED. AN 'R' PREFIX MEANS THE VARIABLE IS RECODED.
*****;

DATA SF36SCAL;
SET SF36DATA;

*****
* THE SF-36 PHYSICAL FUNCTIONING INDEX.
* ALL ITEMS ARE POSITIVELY SCORED -- THE HIGHER THE ITEM
* VALUE, THE BETTER THE PHYSICAL HEALTH.
*
* THIS SCALE IS POSITIVELY SCORED.
* THE HIGHER THE SCORE THE BETTER THE PHYSICAL FUNCTIONING.
*****;

ARRAY PFI(10) PF01-PF10;

DO I = 1 TO 10;
IF PFI(I) < 1 OR PFI(I) > 3 THEN PFI(I) = .;
END;

PFNUM = N(OF PF01-PF10);
PFMEAN = MEAN(OF PF01-PF10);

DO I = 1 TO 10;
IF PFI(I) = . THEN PFI(I) = PFMEAN;
```

END;

IF PFNUM GE 5 THEN RAWPF = SUM(OF PF01-PF10);
PF = ((RAWPF - 10)/(30-10)) * 100;

LABEL PF = 'SF-36 PHYSICAL FUNCTIONING (0-100)'
RAWPF = 'RAW SF-36 PHYSICAL FUNCTIONING';

* THE SF-36 ROLE-PHYSICAL INDEX.
* ALL ITEMS ARE POSITIVELY SCORED -- THE HIGHER THE ITEM VALUE,
* THE BETTER THE ROLE-PHYSICAL FUNCTIONING.
*
* THIS SCALE IS POSITIVELY SCORED.
* THE HIGHER THE SCORE THE BETTER THE ROLE-PHYSICAL.
*****;

ARRAY RPA(4) RP1-RP4;

DO I = 1 TO 4;
IF RPA(I) < 1 OR RPA(I) > 5 THEN RPA(I) = .;
END;

ROLPNUM = N(OF RP1-RP4);
ROLPMEAN = MEAN(OF RP1-RP4);

DO I = 1 TO 4;
IF RPA(I) = . THEN RPA(I) = ROLPMEAN;
END;

IF ROLPNUM GE 2 THEN RAWRP = SUM(OF RP1-RP4);
RP = ((RAWRP - 4)/(20-4)) * 100;
LABEL RP = 'SF-36 ROLE-PHYSICAL (0-100)'
RAWRP = 'RAW SF-36 ROLE-PHYSICAL';

* THE SF-36 PAIN ITEMS.
* ITEM RECODING DEPENDS ON WHETHER BOTH PAIN1 AND PAIN2
* ARE ANSWERED OR WHETHER ONE OF THE ITEMS HAS MISSING DATA.
* AFTER RECODING, ALL ITEMS ARE POSITIVELY SCORED -- THE HIGHER
* THE SCORE, THE LESS PAIN (OR THE MORE FREEDOM FROM PAIN).
*
* THIS SCALE IS POSITIVELY SCORED. THE HIGHER THE
* SCORE THE LESS PAIN OR THE MORE FREEDOM FROM PAIN.
*****;

IF BP1 < 1 OR BP1 > 6 THEN BP1 = .;
IF BP2 < 1 OR BP2 > 5 THEN BP2 = .;

* RECODES IF NEITHER BP1 OR BP2 HAS A MISSING VALUE;

IF BP1 NE . AND BP2 NE . THEN DO;

IF BP1 = 1 THEN RBP1 = 6;

```
IF BP1 = 2 THEN RBP1 = 5.4;
IF BP1 = 3 THEN RBP1 = 4.2;
IF BP1 = 4 THEN RBP1 = 3.1;
IF BP1 = 5 THEN RBP1 = 2.2;
IF BP1 = 6 THEN RBP1 = 1;

IF BP2 = 1 AND BP1 = 1 THEN RBP2 = 6;
IF BP2 = 1 AND 2 LE BP1 LE 6 THEN RBP2 = 5;
IF BP2 = 2 AND 1 LE BP1 LE 6 THEN RBP2 = 4;
IF BP2 = 3 AND 1 LE BP1 LE 6 THEN RBP2 = 3;
IF BP2 = 4 AND 1 LE BP1 LE 6 THEN RBP2 = 2;
IF BP2 = 5 AND 1 LE BP1 LE 6 THEN RBP2 = 1;

END;

* RECODES IF BP1 IS NOT MISSING AND BP2 IS MISSING;

IF BP1 NE . AND BP2 = . THEN DO;
  IF BP1 = 1 THEN RBP1 = 6;
  IF BP1 = 2 THEN RBP1 = 5.4;
  IF BP1 = 3 THEN RBP1 = 4.2;
  IF BP1 = 4 THEN RBP1 = 3.1;
  IF BP1 = 5 THEN RBP1 = 2.2;
  IF BP1 = 6 THEN RBP1 = 1;
  RBP2 = RBP1;
END;

* RECODES IF BP1 IS MISSING AND BP2 IS NOT MISSING;

IF BP1 = . AND BP2 NE . THEN DO;
  IF BP2 = 1 THEN RBP2 = 6;
  IF BP2 = 2 THEN RBP2 = 4.75;
  IF BP2 = 3 THEN RBP2 = 3.5;
  IF BP2 = 4 THEN RBP2 = 2.25;
  IF BP2 = 5 THEN RBP2 = 1;
  RBP1 = RBP2;
END;

BPNUM = N(BP1,BP2);

IF BPNUM GE 1 THEN RAWBP = SUM(RBP1,RBP2);
BP = ((RAWBP - 2)/(12-2)) * 100;

LABEL BP = 'SF-36 PAIN INDEX (0-100)'
      RAWBP = 'RAW SF-36 PAIN INDEX';

*****
* THE SF-36 GENERAL HEALTH PERCEPTIONS INDEX.
* REVERSE TWO ITEMS AND RECALIBRATE ONE ITEM. AFTER RECODING
* AND RECALIBRATION, ALL ITEMS ARE POSITIVELY SCORED -- THE
* HIGHER THE SCORE, THE BETTER THE PERCEIVED GENERAL HEALTH.
*
```

* THIS SCALE IS POSITIVELY SCORED.
* THE HIGHER THE SCORE THE BETTER THE HEALTH PERCEPTIONS.
*****;

ARRAY GHP(5) GH1-GH5;

DO I= 1 TO 5;
IF GHP(I) < 1 OR GHP(I) > 5 THEN GHP(I) = .;
END;

IF GH1 = 1 THEN RGH1 = 5;
IF GH1 = 2 THEN RGH1 = 4.4;
IF GH1 = 3 THEN RGH1 = 3.4;
IF GH1 = 4 THEN RGH1 = 2;
IF GH1 = 5 THEN RGH1 = 1;

RGH3 = 6 - GH3;
RGH5 = 6 - GH5;

GHNUM = N(GH1, GH2, GH3, GH4, GH5);
GHMEAN = MEAN(RGH1, GH2, RGH3, GH4, RGH5);

ARRAY RGH(5) RGH1 GH2 RGH3 GH4 RGH5;

DO I= 1 TO 5;
IF RGH(I) = . THEN RGH(I) = GHMEAN;
END;

IF GHNUM GE 3 THEN RAWGH = SUM(RGH1, GH2, RGH3, GH4, RGH5);
GH = ((RAWGH - 5) / (25-5)) * 100;

LABEL GH = 'SF-36 GENERAL HEALTH PERCEPTIONS (0-100)'
RAWGH = 'RAW SF-36 GENERAL HEALTH PERCEPTIONS';

* THE SF-36 VITALITY ITEMS.
* REVERSE TWO ITEMS. AFTER ITEM REVERSAL, ALL ITEMS ARE
* POSITIVELY SCORED -- THE HIGHER THE SCORE, THE LESS THE FATIGUE
* AND THE GREATER THE ENERGY.
*
* THIS SCALE IS POSITIVELY SCORED.
* THE HIGHER THE SCORE THE GREATER THE VITALITY.
*****;

ARRAY VI(4) VT1-VT4;

DO I = 1 TO 4;
IF VI(I) < 1 OR VI(I) > 5 THEN VI(I) = .;
END;

RVT1 = 6-VT1;
RVT2 = 6-VT2;

VITNUM = N(VT1, VT2, VT3, VT4);
VITMEAN = MEAN(RVT1, RVT2, VT3, VT4);

```
ARRAY RVI(4) RVT1 RVT2 VT3 VT4;
```

```
DO I = 1 TO 4;  
  IF RVI(I) = . THEN RVI(I) = VITMEAN;  
END;
```

```
IF VITNUM GE 2 THEN RAWVT= SUM(RVT1,RVT2,VT3,VT4);  
VT = ((RAWVT-4)/(20-4)) * 100;
```

```
LABEL VT = 'SF-36 VITALITY (0-100)'  
  RAWVT = 'RAW SF-36 VITALITY';
```

```
*****  
* THE SF-36 SOCIAL FUNCTIONING INDEX.  
* REVERSE ONE ITEM SO THAT BOTH ITEMS ARE POSITIVELY SCORED --  
* THE HIGHER THE SCORE, THE BETTER THE SOCIAL FUNCTIONING.  
*  
* THIS SCALE IS POSITIVELY SCORED.  
* THE HIGHER THE SCORE THE BETTER THE SOCIAL FUNCTIONING.  
*****;
```

```
ARRAY SOC(2) SF1-SF2;
```

```
DO I = 1 TO 2;  
  IF SOC(I) < 1 OR SOC(I) > 5 THEN SOC(I) = .;  
END;
```

```
RSF1 = 6 - SF1;  
SFNUM = N(SF1,SF2);  
SFMEAN = MEAN(RSF1,SF2);
```

```
ARRAY RSF(2) RSF1 SF2;
```

```
DO I = 1 TO 2;  
  IF RSF(I) = . THEN RSF(I) = SFMEAN;  
END;
```

```
IF SFNUM GE 1 THEN RAWSF = SUM(RSF1,SF2);  
SF = ((RAWSF - 2)/(10-2)) * 100;
```

```
LABEL SF = 'SF-36 SOCIAL FUNCTIONING (0-100)'  
  RAWSF = 'RAW SF-36 SOCIAL FUNCTIONING';
```

```
*****  
* THE SF-36 ROLE-EMOTIONAL INDEX.  
* ALL ITEMS ARE POSITIVELY SCORED -- THE HIGHER THE ITEM VALUE,  
* THE BETTER THE ROLE-EMOTIONAL FUNCTIONING.  
*  
* THIS SCALE IS POSITIVELY SCORED.  
* THE HIGHER THE SCORE, THE BETTER THE ROLE-EMOTIONAL.  
*****;
```

```
ARRAY RM(3) RE1-RE3;
```

```
DO I = 1 TO 3;
  IF RM(I) < 1 OR RM(I) > 5 THEN RM(I) = .;
END;

ROLMNUM = N(OF RE1-RE3);
ROLMMEAN = MEAN(OF RE1-RE3);

DO I = 1 TO 3;
  IF RM(I) = . THEN RM(I) = ROLMMEAN;
END;

IF ROLMNUM GE 2 THEN RAWRE = SUM(OF RE1-RE3);
RE = ((RAWRE - 3)/(15-3)) * 100;

LABEL RE = 'SF-36 ROLE-EMOTIONAL (0-100)'
      RAWRE = 'RAW SF-36 ROLE-EMOTIONAL';

*****
* THE SF-36 MENTAL HEALTH INDEX.
* REVERSE TWO ITEMS. AFTER ITEM REVERSAL, ALL ITEMS ARE
* POSITIVELY SCORED -- THE HIGHER THE SCORE, THE BETTER THE
* MENTAL HEALTH.
*
* THIS SCALE IS POSITIVELY SCORED.
* THE HIGHER THE SCORE THE BETTER THE MENTAL HEALTH.
*****;

ARRAY MHI(5) MH1-MH5;

DO I = 1 TO 5;
  IF MHI(I) < 1 OR MHI(I) > 5 THEN MHI(I)=.;
END;

RMH3 = 6-MH3;
RMH5 = 6-MH5;

MHNUM=N(MH1,MH2,MH3,MH4,MH5);
MHMEAN=MEAN(MH1,MH2,RMH3,MH4,RMH5);

ARRAY RMH(5) MH1 MH2 RMH3 MH4 RMH5;

DO I = 1 TO 5;
  IF RMH(I) = . THEN RMH(I) = MHMEAN;
END;

IF MHNUM GE 3 THEN RAWMH = SUM(MH1,MH2,RMH3,MH4,RMH5);
MH = ((RAWMH-5)/(25-5)) * 100;

LABEL MH = 'SF-36 MENTAL HEALTH INDEX (0-100)'
      RAWMH = 'RAW SF-36 MENTAL HEALTH INDEX';

*****
* THE SF-36 HEALTH TRANSITION ITEM.
```

```
* THIS ITEM SHOULD BE ANALYZED AS CATEGORICAL DATA,  
* PENDING FURTHER RESEARCH.  
*****;  
  
IF HT < 1 OR HT > 5 THEN HT = .;  
  
LABEL HT='RAW SF-36 HEALTH TRANSITION ITEM';  
RUN;  
  
*****;  
*** STEP 3: SF-36 SCALE CONSTRUCTION ***;  
*****;  
  
DATA SF36INDX;  
SET SF36SCAL;  
  
*****;  
* purpose: create physical and mental health index scores  
* standardized but not normalized  
* and standard deviations calculated with vardef=wdf  
*****;  
  
/*****/  
/* NORM-BASED SCORING OF SF-36, STANDARD RECALL (4 WEEKS) */  
/* USING WEIGHTED MEANS AND SD'S FROM 1998 GENERAL US POPULATION */  
/* FROM COMBINED SAMPLES */  
/*****/  
  
*****  
*****1998 US NORMS*****  
*****;  
  
*CREATING SF-36 STANDARDIZED SCORES (0-100 Means/SD's from 1998 General  
Population)*;  
  
pf_z=(pf-83.29094)/23.75883;  
rp_z=(rp-82.50964)/25.52028;  
bp_z=(bp-71.32527)/23.66224;  
gh_z=(gh-70.84570)/20.97821;  
vt_z=(vt-58.31411)/20.01923;  
sf_z=(sf-84.30250)/22.91921;  
re_z=(re-87.39733)/21.43778;  
mh_z=(mh-74.98685)/17.75604;  
  
*****;  
* COMPUTE SAMPLE RAW FACTOR SCORES *;  
* Z SCORES ARE FROM ABOVE *;  
* SCORING COEFFICIENTS ARE FROM U.S. GENERAL POPULATION *;  
* FACTOR ANALYTIC SAMPLE N=2393: HAVE ALL EIGHT SCALES *;  
*****;
```

```
praw=(pf_z * .42402)+(rp_z * .35119)+(bp_z * .31754)+(sf_z * -.00753)+  
      (mh_z * -.22069)+(re_z * -.19206)+(vt_z * .02877)+(gh_z * .24954);  
  
mraw=(pf_z * -.22999)+(rp_z * -.12329)+(bp_z * -.09731)+(sf_z * .26876)+  
      (mh_z * .48581)+(re_z * .43407)+(vt_z * .23534)+(gh_z * -.01571);  
  
*COMPUTE AGGREGATE STANDARDIZED SUMMARY SCORES*;  
  
PCS = (praw*10) + 50;  
MCS = (mraw*10) + 50;  
  
label PCS='STANDARDIZED PHYSICAL COMPONENT SCALE-00'  
      MCS='STANDARDIZED MENTAL COMPONENT SCALE-00';  
  
run;
```

Appendix I Visit windows based on day ranges

Visit windows based on days relative to the first IMP dose will be used to map the efficacy, lab, vital signs, PK, and immunogenicity data to each scheduled visit (see [Table 7](#)).

Table 7 - Day range for each scheduled visit in the DB period for efficacy, lab, vital sign, PK and ADA summaries

Visit Label	Target Day	Schedule A ^a	Schedule B ^b	Schedule C ^c	Schedule D ^d	Schedule E ^e	Schedule F ^f	Schedule G ^g	Schedule H ^h	Schedule I ⁱ	Schedule J ^j
Double-Blind Period											
Baseline	1	≤ 1	≤ 1	≤ 1	≤ 1	≤ 1		≤ 1	≤ 1	≤ 1	≤ 1
Week 2	15	>1* - 21							>1* - 21	>1* - 49	
Week 4	29	22-42				>1* - 56	>1* - 56	>1* - 42	22 - 56		>1* - 98
Week 8	57	43-70						43 - 70			
Week 12	85	71-98	>1* - 126	>1* - 126		57 - 126	57 - 126	71 - 98	57 - 98	50 - 126	
Week 16	113	99-126						99 - 126	99 - 140		
Week 20	141	127-154						127 - 154			
Week 24	169	155-196	127 - 224	127 - 266		127 - 224	127 - 224	155 - 196	141 - 266	127 - 266	≥ 99
Week 32	225	197-252						197 - 252			
Week 40	281	253-322	225 - 322			225 - 322	225 - 322	253 - 322			
Week 52	365	≥323	≥ 323	≥ 267	>1*	≥ 323	≥ 323	≥ 323	≥ 267	≥ 267	

a Includes temperature, heart rate, blood pressure, PMR clinical assessments (including disease flare), CRP, ESR

b Includes weight, glucocorticoid toxicity index (excluding bone density assessment)

c Includes physician global assessments (MD-VAS), patient reported outcomes and antibodies to sarilumab/ADA

d Includes bone density assessment, ANA

e Includes hematology: hemoglobin, hematocrit, red blood cell (RBC) count and morphology (if RBC count is abnormal), white blood cell (WBC) differential, platelet count, absolute neutrophil count (ANC) and chemistry: sodium, potassium, calcium, chloride, bicarbonate, total protein, creatinine and clearance, blood urea nitrogen (BUN), uric acid, lactate dehydrogenase (LDH), phosphate, albumin, ALT (SGPT), AST (SGOT), alkaline phosphatase (ALP), total bilirubin, conjugated bilirubin, and unconjugated bilirubin

f Includes HbA1c, fasting glucose, fasting lipids: triglycerides (TG), total cholesterol, HDL, LDL

g Includes urine pregnancy test

h Includes serum sarilumab

i Includes biomarkers-IL-6 and sIL-6R

j Includes immune cell phenotyping (whole blood)

* Includes value measured on day 1 but after the first IMP dose

For PK and ADA, the follow-up (i.e., 6-week post-treatment) measurement will be defined based on the sample collected at the follow-up visit (ie, Visit 13). The rest of PK and ADA measurements will be mapped to each visit using the visit window defined in [Table 7](#).

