
ENDPOINT(S)
	
Primary endpoint:
 
Proportion of patients achieving sustained remission at Week 52. Sustained remission at Week 52 is defined by having met all of the following parameters:
 
 
• Achievement of disease remission no later than Week 12, AND
 
• Absence of disease flare from Week 12 through Week 52, AND
 
• Sustained reduction of CRP (to <10 mg/L, with an absence of successive elevations to ≥10 mg/L) from Week 12 through Week 52, AND
 
• Successful adherence to the prednisone taper from Week 12 through Week 52.
 
 
Disease remission is defined as resolution of signs and symptoms of PMR, and normalization of CRP (<10 mg/L).
 
Note: A single CRP elevation (≥10 mg/L) is not considered absence of remission unless CRP remains elevated (≥10 mg/L) at 2 consecutive study visits.
 
Flare is defined as recurrence of signs and symptoms attributable to active PMR requiring an increase in CS dose, or elevation of ESR attributable to active PMR plus an increase in CS dose. Increase in CS dose is defined as:
 
 
• Any dose increase during the protocol defined steroid taper.
 
• Re-initiation of prednisone therapy after the protocol defined taper has been completed.
 
 
Note: During the initial 12 weeks of prednisone taper, treatment for one flare before Week 12 is permitted if it can be successfully treated with a ≤5 mg/day prednisone add-on taper regimen (completed prior to Week 12) and provided that all other sustained remission parameters are met.
 
Secondary endpoint(s):
 
Efficacy:
 
 
• Summary of the components of sustained remission at Week 52.
 
• Total cumulative prednisone dose (or equivalent) over 52 weeks.
 
• Time to first PMR flare
 
• Changes from baseline in GTI (and components)
 
 
Safety:
 
 
• Adverse events (AEs), laboratory values (including antidrug antibody [ADA], vital signs).
 
 
Pharmacokinetic
 
 
• Serum concentrations of sarilumab.
 
 
Other efficacy endpoint(s):
 
 
• Change from baseline in the Physician global assessment of disease activity- visual analog scale (MD-VAS).
 

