	
permanent discontinuation and TB, and potential opportunistic infections.
 
A dual assessor approach will be required in order to maintain the blind during the double-blind treatment period with sarilumab, prednisone and matching placebos. The Efficacy Assessor should be a rheumatologist or other skilled PMR assessor and may be the principal investigator who will be responsible for completing the overall evaluation and management of PMR disease activity. The Safety Assessor should be a physician who will be responsible for assessing and managing any safety concerns related to the patient during the course of the study including reviewing the patient's laboratory data and assessing/reporting/managing any AEs. The Safety Assessor cannot be the Efficacy Assessor.
 
Patients and Investigators must respect the visit schedule per study flow chart. If a visit date is changed, the next visit should take place according to the original schedule.
 
Blood samples in a subset of patients will be collected to evaluate circulating immune cell phenotypes.

STATISTICAL CONSIDERATIONS
	
Sample size determination: There are no prior controlled study data to establish the placebo remission rate in PMR. The sample size of 59 per group provides at least 85% and 95% power to detect 25% and 30% treatment difference respectively, assuming 5% to 15% placebo response rate, and using a significance level of 0.05.
 
Analysis population: The primary efficacy analysis population will be the intent-to-treat (ITT) population, which consists of all randomized patients. All patients will be analyzed according to the treatment to which they are randomized.
 
The safety population will include all randomized patients who have received at least one dose or part of a dose of the study medication. All patients will be analyzed according to the treatment they have actually received.
 
Primary analysis: The proportion of patients in sustained remission at Week 52 will be analyzed using 2-sided Fisher's exact test. A significance level of 0.05 will be used.
 
Analysis of secondary endpoints: Other binary endpoints will be analyzed using the same approach as the primary analysis. Total cumulative prednisone (or equivalent) dose will be analyzed by Wilcoxon rank-sum test. Time to event analysis will use Kaplan-Meier estimates and a log rank test.

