1.6 STATISTICAL MODIFICATIONS MADE IN THE STATISTICAL ANALYSIS PLAN

Due to the premature termination of the study, a total of 118 patients (42%) of the 280 patients planned were randomized. The randomized patients could continue in the study to complete the treatment period and the 6 weeks post-treatment follow up per protocol. Hence, there are no changes to the efficacy analysis plan per protocol.

The COVID-19 pandemic has also impacted data collection as patients may not be able to visit clinical sites for endpoint assessments. Additional patient level information at visits that were impacted by the pandemic situations were captured for assessments performed in visits that were delayed, not done, partially done on site, or partially done by phone. Major or critical COVID-19 impacted deviations per protocol were also recorded.

To assess the impact of the pandemic on the study, COVID-19 related summaries are added as below.

- a) Patients who permanently discontinue study treatment or study due to COVID-19 reasons will be summarized in patient disposition table
- b) Patient disposition by visit according to trial impact due to COVID-19
- c) Critical or major deviations summary according to COVID-19 impact
- d) Number (%) of patients experiencing at least one treatment-emergent COVID-19 related adverse event by primary SOC and PT

In addition, if > 10% patients are impacted by the COVID-19 pandemic, below summaries/analyses will be generated by COVID-19 impacted population (Yes, No):

- a) Extent of exposure to SC IMP
- b) Treatment compliance for SC IMP

- c) Number (%) of patients with TEAEs by primary SOC and PT, and
- d) Analysis of the primary endpoint of sustained remission at Week 52.

The population with and without trial impact (disruption) due to COVID-19 is defined in [Section 2.3.4](#).

In addition, upon meeting with Japan Health Authorities (PMDA) in April 2019, data for the components to calculate the PMR activity score (PMR-AS) were subsequently collected and the analysis plan is described in [Section 2.4.4.3](#).

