Note that during the initial 12 weeks of prednisone taper, treatment for one flare before Week 12 is permitted if it can be successfully treated with a low dose (≤ 5 mg/day) prednisone add-on taper regimen (completed prior to Week 12) and provided that all other sustained remission parameters are met.

2. Absence of disease flare from Week 12 through Week 52.

Flare is defined as either 1) recurrence of signs and symptoms attributable to active PMR plus an increase in CS dose due to PMR, or 2) elevation of ESR attributable to active PMR plus an increase in CS dose due to PMR. Increase in CS dose is defined as:

- Any dose increase during the protocol defined steroid taper, or
- Re-initiation of prednisone therapy after the protocol defined taper has been completed.

Patients with disease flare are identified as those with the reason for treatment ticked “rescue therapy” in eCRF “Steroid Medication” page and to the question “If Rescue Therapy, please specify” ticked either “Active PMR” or “Elevated ESR Attributable to Active PMR”.

3. Sustained reduction of CRP (to <10 mg/L, with an absence of successive elevations to ≥10 mg/L) from Week 12 through Week 52

The status of normalization of CRP from Week 12 through Week 52 will be determined based on the CRP values measured at Week 16, Week 20, Week 24, Week 32, Week 40 and Week 52. If there are two or more consecutive visits with CRP ≥10 mg/L, then it is categorized as no normalization of CRP. Intermittent missing CRP at Week 16, Week 20, Week 24, Week 32, Week 40 or Week 52 will be imputed using last value carried forward (LOCF) approach up to the last non-missing measurement.

4. Successful adherence to the prednisone taper from Week 12 through Week 52

Successful adherence to the prednisone taper from Week 12 through Week 52 is defined as patients who did not take rescue therapy from Week 12 through Week 52 and any excess prednisone (beyond the per protocol CS tapering regimen) with a cumulative dose of ≤100 mg (or equivalent), such as those employed to manage AE not related to PMR. The cumulative dose of excess prednisone use will be counted from baseline to Week 52 (does not include add-on prednisone taken prior to Week 12).

In addition, patients who permanently withdraw from the study treatment prior to Week 52 will be considered as not having achieved component 2, 3, or 4 for the primary endpoint.

Blinding of CRP and ESR assessment results

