2.5.4 Windows for time points

Visit windows based on days relative to the first IMP dose will be used to map the efficacy, lab, vital signs, PK and ADA measurements to each scheduled visit (see [Appendix I](#)). The following rule will be applied when mapping the measurements to the visit:

- For the same parameter (i.e., efficacy, lab, or vital signs), if a patient has more than one measurement at different dates within the same visit window, the scheduled measurement that is closest to the target date will be used (in case of tie select the latest). If there is no scheduled measurement within the visit window, the unscheduled measurement that is closest to the target date will be used (in case of tie select the latest).
- When a patient has more than one measurement on the same parameter on the same date, then the one with the later/largest sample ID will be used.
- If there is no measurement for a given parameter in an analysis window, data will be considered missing for the corresponding visit.

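### The SAP's day windows can drop a measured CRP when a visit is well overdue, so component 3 of sustained remission can be scored wrongly in either direction, though probably rarely

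*SAP*

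**What the plan says.** **Endpoint rule.** SAP 2.1.3.1 judges component 3 on CRP at Weeks 16, 20, 24, 32, 40 and 52: "If there are two or more consecutive visits with CRP ≥10 mg/L, then it is categorized as no normalization of CRP". Intermittent missing values are filled by last value carried forward. The protocol's component 3 speaks of successive elevations. Its note on CRP, attached to the definition of disease remission, counts an elevation only when it persists "at 2 consecutive study visits".

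**Mapping rule.** SAP 2.5.4 states: "Visit windows based on days relative to the first IMP dose will be used to map the efficacy, lab, vital signs, PK and ADA measurements". When several values fall in one window, "the scheduled measurement that is closest to the target date will be used (in case of tie select the latest"). For an empty window, "If there is no measurement for a given parameter in an analysis window, data will be considered missing for the corresponding visit".

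**Windows.** The footnote to Table 7 Schedule A (SAP Appendix I) reads: "Includes temperature, heart rate, blood pressure, PMR clinical assessments (including disease flare), CRP, ESR". The windows are Week 16 Days 99-126, Week 20 Days 127-154, Week 24 Days 155-196, Week 32 Days 197-252, Week 40 Days 253-322, and Week 52 Day 323 onwards.

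**Late visits.** The Protocol Clinical Trial Summary says: "If a visit date is changed, the next visit should take place according to the original schedule". SAP 1.6 records COVID-19 disruption, including "visits that were delayed, not done, partially done on site, or partially done by phone".

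**The concern.** The endpoint is defined on visits, but the data reach it through day windows. After a long delay the next visit keeps its date, so two scheduled CRPs can fall in the same window. Only one survives. The visit that loses its value is treated as missing although blood was drawn and assayed, and carry-forward may then replace the measured result with an older one.

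Component 3 is a required part of the primary endpoint. With 59 patients per arm, each patient whose endpoint status changes moves that arm's rate by 1/59 = 1.7 percentage points. Near the significance boundary a single patient can decide Fisher's exact test: 16 against 6 responders gives p = 0.032, 16 against 7 gives 0.061, and 15 against 6 gives 0.052. These counts show sensitivity only; they are not forecasts.

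**Working it through.** **1. Reproduce the windows.** Each Schedule A window starts at the midpoint of adjacent target days, and the midpoint day goes to the later visit:
- Week 16: (85 + 113)/2 = 99
- Week 20: (113 + 141)/2 = 127
- Week 24: (141 + 169)/2 = 155
- Week 32: (169 + 225)/2 = 197
- Week 40: (225 + 281)/2 = 253
- Week 52: (281 + 365)/2 = 323

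All match Table 7.

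**2. Delay needed to leave the window** (start of the next window minus the visit's own target day):
- Week 16: 127 - 113 = 14 days
- Week 20: 155 - 141 = 14 days
- Week 24: 197 - 169 = 28 days
- Week 32: 253 - 225 = 28 days
- Week 40: 323 - 281 = 42 days

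A late Week 52 visit is never lost, because its window is open-ended.

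**3. Wrong pass.** Suppose CRP is 4 on Day 113, 15 on Day 156 (the Week 20 visit, 15 days late), 12 on Day 169, then normal. Days 156 and 169 both fall in 155-196. Their distances from target are |156 - 169| = 13 and 0, so the 15 is dropped. Week 20 is empty and takes 4 by carry-forward. The scored series is 4, 4, 12, then normal: a pass, although two consecutive study visits were elevated. Without carry-forward it is 4, missing, 12, then normal, which still passes. Windowing alone is enough.

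**4. Wrong fail.** Suppose CRP is 15 on Day 113, 4 on Day 156, 4 on Day 169, then normal. The Day 156 value is dropped and Week 20 takes 15 by carry-forward. The scored series is 15, 15, 4, then normal: a fail, although only one CRP was elevated. This direction needs windowing and carry-forward together.

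**5. All patterns.** The written rules were applied to all 2^7 = 128 high/normal patterns over Weeks 12 to 52, with one late visit and the others on target, and compared with the same test on the CRPs as measured. Carry-forward was allowed to start from Week 12, which matters only when Week 16 is late.

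| Late visit | Days late | Wrong passes | Wrong fails |
|---|---|---|---|
| Week 16 | 14 | 5 | 5 |
| Week 20 | 14 | 6 | 16 |
| Week 24 | 28 | 8 | 10 |
| Week 32 | 28 | 6 | 12 |
| Week 40 | 42 | 10 | 12 |

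With each visit one day less late there are no errors. These are counts of patterns, not probabilities. If the late value lies nearer the target than the next visit's value (for example Day 168 against Day 172), the next visit's CRP is dropped instead.

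**6. Size under assumed inputs.** The documents give neither delay lengths nor CRP elevation rates, so every input here is an assumption.
- 5-20% of visits 14-35 days late and 10-30% of CRPs elevated, autocorrelated: component 3 wrong in 0.7% to 5.3% of patients, or 118 x 0.007 = 0.8 to 118 x 0.053 = 6.3 patients.
- 1-2% of visits that late, or 2% of CRPs elevated: 0.1% to 0.5%, or 118 x 0.001 = 0.1 to 118 x 0.005 = 0.6 patients.

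**The case against.** **Table 7 is only for summaries.** Its title says so, but SAP 2.5.4 is a general data-handling rule that names efficacy data, and nothing exempts CRP or the primary endpoint. If nominal visits were intended, the SAP should say so.

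**All measurements will be used.** SAP 2.5.6 says this about remote and local assessments. It gives no rule for two values in one window.

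**Visits have a ±3-day window (Protocol 10.2).** Correct: visits within that window, and any visit up to 13 days late, are unaffected. The error needs a long delay and a next-visit CRP in the same window. This limits the frequency but does not correct the rule.

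**Other analyses bound the exposure.** The sensitivity analysis without acute phase reactants (SAP 2.4.4.1) removes CRP altogether, so this error cannot affect it. It does not repair the primary result. The tipping-point analysis varies only withdrawn patients without a flare. The COVID-19 subgroup analysis runs only if more than 10% of patients are affected, and it would use the same scored endpoint.

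**One value per window is a common convention, and two draws 13 days apart may not show a sustained elevation.** This is fair as a clinical judgement. But the plan's test is on consecutive visits, with no minimum spacing.

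**Stronger readings.** A reader might infer that up to six patients change primary endpoint status, or that the error favours one arm. The documents support neither. The upper figure counts component 3 errors, not endpoint changes. It also rests on a model that lets a Week 16 or 20 visit run 28-35 days late, which puts it on or after the next visit (28 days later), so it is on the generous side. On direction, SAP 2.4.4.1 notes sarilumab's effect on acute phase reactants, so elevations may be rarer in that arm. But errors run both ways and no rates by arm are given, so the net direction is unknown.

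**Conclusion.** The rule is wrong as written, and the error is probably rare. SAP 2.5.4, Table 7 Schedule A and SAP 2.1.3.1, read with the protocol's scheduling rule, can drop a measured scheduled CRP and score component 3 against the plan's own consecutive-visit test. A wrong pass needs only the windows; a wrong fail also needs carry-forward.

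The effect cannot be sized from the documents, because the number and length of delays are not stated. Across assumed inputs of 1-20% of visits at least 14 days late and 2-30% of CRPs elevated, it runs from well under 1 to about 6 component 3 errors in 118 patients. Fewer will change the primary endpoint, since the patient must also meet the other three components; for example, a patient who took rescue therapy from Week 12 on fails component 4 regardless of CRP. The sample size and power figures are not affected. The change is worth making because it touches a required component of the primary endpoint and costs little.

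**What to change.** In SAP 2.1.3.1, component 3, add a statement to this effect: the test for two or more consecutive visits is applied to the measured CRP values of the scheduled visits, by nominal (eCRF) visit in date order; no measured scheduled CRP is dropped or replaced because of its day window; a visit is missing, and falls under the existing missing-data rule, only when no CRP was measured for it.

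Leave the handling of unscheduled values as it is, and keep Table 7 Schedule A for by-visit CRP summaries.

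The cost is that statement and a small programming change. The downside is that two visits counted as consecutive may be less than two weeks apart when one of them is late.
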